## **Statistical analysis**

Statistical analyses will be performed using JMP 16 software (SAS Institute, Cary NC).

Significance level will be set to 0.05 for all analyses. Descriptive statistics (i.e., mean, standard deviation (SD)) will be used to summarize demographic characteristics of participants and study outcomes. Shapiro-Wilk tests will be used to examine if the data was normally distributed.

Primary analyses will utilize two-way repeated-measures ANOVAs to examine the effects of tDCS on dual-task cost to standing and sway outcomes. The dependent variable of each model is the primary outcomes of standing (i.e., dual task cost to sway speed and area) and walking (i.e., dual task cost to walking speed). Similar analyses will be applied to the secondary outcomes such as (dual task cost to gait stride time variability, and the walking speed and stride time variability within each condition). Model effects will include stimulation condition (i.e., gel-tDCS, sponge-tDCS, gel-sham and sponge-sham), time (pre-, post-stimulation), and their interaction. Age, sex, and BMI will be included as covariates because each is associated with one or more metrics of standing or walking. Tukey's post-hoc testing will be used to compare factor means of significant models.

A secondary exploratory analysis using one-way ANOVAs to compare the effects of the stimulation conditions on the percent changes of the standing and walking outcomes will be performed. Model effect will be stimulation condition.

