Standing and walking are almost always completed in unison with other cognitive tasks such as talking, reading or making decisions. The ability to perform this important type of “dual tasking” is critical to daily activities and dependent upon one’s capacity to effectively activate appropriate brain networks that include the left dorsolateral prefrontal cortex (dIPFC). Transcranial direct current stimulation (tDCS) is a safe, noninvasive technology that can selectively modulate brain excitability (i.e., the likelihood of activation) by passing low-level currents between electrodes placed upon the scalp. We have demonstrated through a series of studies that a single, 20-minute exposure of ‘conventional’ tDCS targeting the left dIPFC—administered via two large sponge electrodes—reduces dual task costs to metrics of standing postural control and gait, when tested immediately following stimulation. Still, we and others have also observed relatively high between-subject variability in the effects of this conventional bipolar form of tDCS. We contend that this variability in effectiveness arises in part from relatively diffuse and unspecific current flow when using large sponge electrodes, in combination with individual variability in head and brain anatomy that significantly alters current flow and the generated electric field in the target brain region. In this project, we will 1) apply recent advances in tDCS modeling and administration to model the electric fields generated by conventional tDCS in older adults using their individual structural brain MRIs, and 2) develop and test an multi-channel tDCS montage designed to optimize current flow to the left dIPFC (i.e., ‘optimized’ tDCS). Our Specific Aim is to examine the immediate after-effects of conventional tDCS, optimized tDCS, and sham stimulation on dual task standing and walking in older adults. Our study population will be older men and women without overt disease or illness, yet with poor baseline dual task performance defined as a dual task cost (i.e., reduction) to gait speed of at least 10% induced by simultaneously performing a serial subtraction task when walking. We hypothesize that across participants, the effect of conventional tDCS on dual task standing and walking performance will correlate with a specific component of the electric field generated over the left dIPFC target. We also hypothesize that optimized tDCS will induce A) greater effects on dual task standing and walking performance as compared to conventional tDCS and sham stimulation, and B) these effects will be more consistent across individuals as compared to conventional tDCS. This project will provide important insights into tDCS “dosage” that will enable us and many other researchers to better understand, control, and optimize this form of noninvasive brain stimulation to individual head and brain anatomy. It is also expected to demonstrate that optimized tDCS, as compared to the conventional approach, significantly improves the size and consistency of observed benefits to dual task standing and walking in vulnerable older adults.

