The immediate after-effects of conventional tDCS on dual task walking performance are beneficial yet relatively variable across older adults with high baseline dual task costs to gait speed. We extracted data from all older adult participants described in the previous section who had “at-risk” baseline dual task costs to gait speed of $>20\%$ despite no overt disease or illness ($n=20$; 12 women; dual task cost $\mu\pm\sigma=26\pm13\%$; age= 75 ± 6 years). Conventional tDCS targeting the left dlPFC reduced the dual task cost to gait speed in all but one participant, and at the group level, significantly reduced this outcome as compared to sham stimulation ($p=0.002$). While the mean absolute pre-to-post change in dual task cost from pre-to-post tDCS was 12 percentage points, the standard deviation of change was 10 with a range of 35. These data demonstrate that 1) we can recruit older adults with poor dual task performance, 2) conventional tDCS holds promise to improve dual task performance in these vulnerable individuals, and 3) the effects of tDCS, while beneficial, are quite variable across individuals.

The degree to which conventional tDCS is “on-target” correlates with dual task improvements, yet varies across participants. We completed a pilot RCT in which 20 older adults with slow gait and mild-to-moderate executive dysfunction, yet who were without overt disease or illness, were randomized to a 2- week, 10-session conventional tDCS intervention targeting the left dlPFC (NCT02436915).⁵⁶ tDCS, compared to sham, reduced dual task costs to gait speed and postural sway speed, and improved cognition as assessed by the Montreal Cognitive Assessment (MoCA), at a two-week follow-up ($p<0.05$). Twelve participants also completed a baseline structural brain MRI. Six of these were then randomized to tDCS. We used Stimweaver with each MRI to model generated electric fields based upon the electrode placement and flow parameters used for the intervention. The normal component of the electric field (nE) averaged over the left dlPFC varied considerably, and, correlated closely with reduced dual task costs to gait speed at follow-up ($r^2=0.80$, $p<0.05$). In contrast, the nE over the right dlPFC did not correlate with dual task changes (not shown). These data give us confidence that the left dlPFC is an important target for dual task performance, and optimizing tDCS will likely maximize its effectiveness and reduce inter-subject variability.

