Specific Aim: To conduct a “within-subject” cross-over study to determine the acute effects of single sessions of optimized tDCS, conventional tDCS, and sham stimulation on dual task standing and walking in 30 older adults who are free of overt disease yet who present with poor baseline dual task performance.

Hypothesis 1: Across participants, the effect of conventional tDCS on dual task standing and walking performance will significantly correlate with the average of the nE component over the left dlPFC.

Hypothesis 2: Optimized tDCS will induce A) greater improvements on dual task standing and walking performance as compared to conventional tDCS and both sham conditions, and B) these effects will be more consistent across individuals as compared to conventional tDCS.

Study Design

We will conduct a “within-subject,” double-blinded, randomized controlled study comparing the after-effects of single sessions of conventional tDCS, optimized tDCS, and two different sham conditions on dual task performance in men and women aged 65-85 years with poor baseline dual task performance. Participants will have the option to complete a structural and functional brain MRI. They will complete four visits during which they will receive one of the four interventions in random order. Visits will be separated by one week to ensure washout of tDCS effects on brain physiology. Dual tasking will be tested before tDCS, after tDCS and again one hour later.

Study Duration (total)

One year

Study Duration for participants

Up to 8 weeks

Participant Selection

Participants will be recruited from the Boston area community, senior housing facilities in urban and suburban areas, research recruitment repositories including the "Mobility and Brain Function" repository, multiple clinics at the BIDMC, and advertisements within regional media outlets and website posting (IFAR and clinicaltrials.gov).

We aim to obtain complete datasets in 30 participants. We expect to enroll 36 individuals to achieve this aim.

Inclusion criteria

- Men and women aged 65-85 years;
- Poor dual task performance, defined as a preferred gait speed that is >10% slower when walking and simultaneously performing verbalized serial subtractions (i.e., dual tasking), as compared to walking normally (i.e. single tasking).

Exclusion criteria

- Unwillingness to cooperate or participate in the study protocol;
- An inability to walk or stand for 30 continuous seconds without an assistive device;

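### Adjusting for each visit's pre-stimulation value uses data already collected and may be more precise than the SAP's change-score comparison, by an amount the documents do not fix

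*SAP*

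**What the plan says.** The SAP's only section, Statistical analysis, makes a two-way repeated-measures ANOVA the primary analysis for each dual task cost. Its terms are given as: "Model effects will include stimulation condition (i.e., gel-tDCS, sponge-tDCS, gel-sham and sponge-sham), time (pre-, post-stimulation), and their interaction". Pre-stimulation values therefore enter as rows of the outcome. The covariates are person-level: "Age, sex, and BMI will be included as covariates because each is associated with one or more metrics of standing or walking". An exploratory one-way ANOVA on percent change has condition as its only effect. Pairwise follow-up is by Tukey's method, and only where a model is significant. No analysis in the SAP uses the pre-stimulation value as a covariate.

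The protocol's opening summary states the aim as to "examine the immediate after-effects of conventional tDCS, optimized tDCS, and sham stimulation on dual task standing and walking in older adults". Under Study Objectives, Aims and Hypotheses, Hypothesis 2A expects optimized tDCS to give "greater improvements on dual task standing and walking performance as compared to conventional tDCS and both sham conditions". Each participant receives all four conditions in random order. Study Design and the pre/post assessment text under Study Procedures have dual tasking tested before stimulation at each of these visits. On size, Participant Selection says: "We aim to obtain complete datasets in 30 participants".

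**The concern.** Averaged over pre and post, the condition main effect dilutes a stimulation effect, and the time main effect is common to all conditions. The stimulation effect is isolated only by condition by time, which is a comparison of changes. A change score subtracts the whole pre-stimulation value, although the most precise amount to subtract depends on how strongly pre and post values move together within a visit. If they move together only moderately, full subtraction adds noise.

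The covariate that could reduce this noise is the visit's own pre-stimulation value. Age, sex and BMI do not vary across a person's visits, so as additive terms with complete data they cannot sharpen a within-person contrast. The SAP does not claim that they do. What is at stake is the precision of the three Hypothesis 2A comparisons with a target of 30 complete datasets.

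**Working it through.** **Inputs.** The target is 30 complete datasets from 36 enrolled (Participant Selection), an implied loss of 6/36 = 16.7%. No power, target effect or SD is attached to that number, so the plan has no precision figure to reproduce. The nearest figures are under Previous Studies: in 20 older adults selected for a gait-speed cost above 20%, the baseline SD was 13 points and, for the pre-to-post change under conventional tDCS, "the standard deviation of change was 10 with a range of 35". Neither document gives rho.

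**Step 1: the interaction is a change-score comparison.** On simulated data (30 people, 4 conditions, pre and post), condition by time gave F = 9.398 on 3 and 87 df. A one-way repeated-measures ANOVA on post minus pre gave the same F and the same df. In a random-intercept mixed model, the interaction coefficient and the difference in mean changes were both 0.9360.

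**Step 2: the weight on the pre value.** Let pre and post have equal within-person variance s² and correlation rho within a visit. The variance of post − b·pre is s²(1 + b² − 2b·rho).

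- Change score (b = 1): 2s²(1 − rho).
- Best weight (b = rho): s²(1 − rho²).
- Ratio: (1 + rho)/2.

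| rho | 0 | 0.3 | 0.5 | 0.7 | 0.9 | 1 |
|---|---|---|---|---|---|---|
| Variance ratio | 0.50 | 0.65 | 0.75 | 0.85 | 0.95 | 1.00 |
| CI width ratio (square root) | 0.71 | 0.81 | 0.87 | 0.92 | 0.97 | 1.00 |

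**Step 3: what the earlier SDs can and cannot fix.** With equal pre and post SDs, the total correlation is 1 − 100/(2 × 169) = 0.70. This mixes stable differences between people with visit-to-visit variation, and only the latter sets rho in a crossover. Error variance is 100/2 = 50 and the remaining variance is 169 − 50 = 119. If a share f of the 119 is visit-to-visit (assumption), rho = 119f/(119f + 50).

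| f | 0 | 0.25 | 0.50 | 0.75 | 1 |
|---|---|---|---|---|---|
| rho | 0 | 0.37 | 0.54 | 0.64 | 0.70 |
| Ratio, theory | 0.50 | 0.69 | 0.77 | 0.82 | 0.85 |
| Ratio, simulated at n = 30 | 0.51 | 0.70 | 0.78 | 0.85 | 0.87 |

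The simulation used 6,000 trials per setting and estimated the within-person slope. Both estimators were unbiased. Estimating the slope costs 0.01 to 0.03 on the ratio.

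**Step 4: response that varies between people.** Let h be extra response variance in each active condition, independent of baseline and of the other condition, and e the pre and post error variance, with 2e + h = 100. For optimized v conventional, the ratio is [e(1 + rho) + h]/(2e + h). Example: h = 50 gives e = 25. With all remaining variance visit-to-visit, rho = 144/169 = 0.85, and the ratio is (25 × 1.85 + 50)/100 = 0.96.

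| h (assumption) | 0 | 25 | 50 | 75 |
|---|---|---|---|---|
| All remaining variance visit-to-visit | 0.85 | 0.92 | 0.96 | 0.99 |
| Half visit-to-visit | 0.77 | 0.86 | 0.94 | 0.98 |
| None visit-to-visit (rho = 0) | 0.50 | 0.63 | 0.75 | 0.88 |

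Simulated values for the first row were 0.86, 0.93, 0.98 and 1.00. No simulated setting put adjustment materially behind the change score.

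**Step 5: scale in points, for illustration only.** Assume a change SD of 10 in every condition, changes independent across visits, n = 30, two-sided 5% and 80% power, with no multiplicity adjustment. The standard error is √2 × 10/√30 = 2.58, and the detectable pairwise difference is (1.96 + 0.84) × 2.58 = 7.2 points. A ratio of 0.50 makes it 7.2 × 0.71 = 5.1, a ratio of 0.85 makes it 6.7, and a ratio of 1.00 leaves it at 7.2.

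**The case against.** The strongest reply is that nothing is wrong. The planned contrast is unbiased under random order, the documents promise no power or precision, and so no stated figure becomes false. The protocol itself says that "the effects of tDCS, while beneficial, are quite variable across individuals", which is the setting in which the gain shrinks. On the confidence-interval scale, a variance ratio of 0.92 is only about 0.96. The only relevant SDs cover gait speed after active tDCS in a selected group, and nothing anchors the sway outcomes. All of this stands. It limits what may be claimed about size, but it does not remove the case for a near-free adjustment that showed no material loss.

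A second reply concerns cost. A model of post on pre drops any visit without a pre value, whereas a mixed-model fit of the SAP's layout can keep the post row. The protocol's risk section lets participants skip tests, so this can happen. It also stands, and it is why the planned analysis should be kept alongside.

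A reader might also infer that the adjustment is needed to obtain the Hypothesis 2A comparisons, because condition then becomes the single treatment term and Tukey's six pairs contain all three. That is a convenience only. A repeated-measures model of post-minus-pre change gives the same six pairs, so it is no argument for adjustment.

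**Conclusion.** The point holds as a missed opportunity for precision. Relative to the planned comparison of changes, the variance of a condition contrast after adjustment could lie anywhere from about 0.50 (rho = 0) to about 1.00 (rho near 1, or strong variation in response between people). That is a confidence-interval width ratio of about 0.71 to 1.00. The (1 + rho)/2 result assumes equal pre and post SDs and no response heterogeneity, and the range takes rho as non-negative.

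Two stronger readings are not supported. One is that the SAP's analysis is biased or invalid: with randomised order, the interaction estimates the intended effect. The other is that the earlier SDs of 13 and 10 imply a gain of 15%. That figure treats all stable variance as visit-to-visit and all variation in change as error, and the documents support neither assumption. No single percentage should be quoted.

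**What to change.** For each primary outcome, make the primary model a linear mixed model of the immediate post-stimulation dual task cost on condition and that visit's pre-stimulation dual task cost, with a participant random effect. Split the pre value into the participant's mean and the visit's deviation from it, so that the slope on the deviation is the within-person one. Name condition as the decisive term and apply Tukey to the four condition means.

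Keep the planned condition-by-time analysis as a sensitivity analysis. It reports within-condition change and, fitted as a mixed model, retains visits with a missing pre value.

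The cost is SAP wording, one degree of freedom for the within-person slope, and the loss from the primary model of any visit without a pre value. No new measurement is needed.

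### The SAP's Tukey follow-up contains no test of Hypothesis 2A's three differences in improvement, and nothing links H2A to a named test

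*SAP*

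**What the plan says.** The protocol (Study Objectives, Aims and Hypotheses) states Hypothesis 2A as: "Optimized tDCS will induce A) greater improvements on dual task standing and walking performance as compared to conventional tDCS and both sham conditions". Reading optimized as gel and conventional as sponge, these are three differences in improvement: gel-tDCS against sponge-tDCS, against gel-sham and against sponge-sham.

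The SAP (Statistical analysis) says: "Primary analyses will utilize two-way repeated-measures ANOVAs to examine the effects of tDCS on dual-task cost to standing and sway outcomes". It continues: "Model effects will include stimulation condition (i.e., gel-tDCS, sponge-tDCS, gel-sham and sponge-sham), time (pre-, post-stimulation), and their interaction". The follow-up is one sentence: "Tukey's post-hoc testing will be used to compare factor means of significant models". It does not say which effect must be significant, which means are compared, or which result supports H2A. Significance is 0.05 throughout.

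The only planned analysis with change as its outcome is labelled secondary and exploratory: "one-way ANOVAs to compare the effects of the stimulation conditions on the percent changes of the standing and walking outcomes". Condition is its sole effect and no pairwise comparison is named.

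**The concern.** H2A is the trial's comparative claim. A difference in improvement between two conditions involves four means: pre and post under each. Tukey compares means two at a time. A significant interaction therefore leads to a follow-up that cannot state the hypothesis, and the analyst must choose a substitute: post-versus-post pairs, condition means, within-condition pre-versus-post pairs, or contrasts formed later. Both the power for H2A and what would count as success depend on that choice, which the plan leaves open.

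**Working it through.** **Structure (no assumptions needed).** Four conditions by two times give 8 cells and 8×7/2 = 28 Tukey pairs: 4 pre-versus-post within a condition, 12 between conditions at the same time, and 12 mixed. None is a difference of changes. Condition means average pre and post, so a difference in change of d appears as d/2. Time means ignore condition. The interaction tests whether the four changes are equal, but without direction. In simulation it was significant in 99.5–100% of trials when gel- and sponge-tDCS both improved by 12 points and the shams by 0, where H2A is false.

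**Inputs.** The plan gives no power figure to reproduce. From the protocol's previous-studies section: mean change 12 points, change SD 10, baseline SD 13. These are dual task cost to gait speed in 20 people with baseline cost above 20%. This trial enrols on poor performance "defined as a preferred gait speed that is >10% slower when walking". Assumed: n = 30 complete, shams 0, equal SDs, independent visits, two-sided 0.05, no covariate effects, and gel 12 against sponge 6.

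**Variances.** Change SD 10 gives residual variance 10²/2 = 50 per assessment. Let ρ be the within-participant correlation of pre and post at one visit. Visit variance is v = 50ρ/(1−ρ). Participant variance is 169 − 50 − v. So ρ cannot exceed 119/169 = 0.70.

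Per-participant variance of a two-condition contrast:
- post values only: 2(50 + v) = 100/(1−ρ)
- change: 2×100 = 200
- post adjusted for pre: 100(1+ρ)

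Adjustment is never worse than either alternative in this formula. Post-only beats change when ρ is below 0.5.

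**Hand check, gel against sponge (the limiting contrast).**
- Tukey, critical value q(8, 203)/√2 = 3.06. At ρ = 0: SE = √(100/30) = 1.83, 6/1.83 = 3.29, Φ(3.29 − 3.06) = 59%. At ρ = 0.28: v = 19.4, expected pooled error 50 + 2×19.4×87/203 = 66.7, threshold 3.06×√(2×66.7/30) = 6.45, true SE √(138.9/30) = 2.15, Φ((6 − 6.45)/2.15) = 42%.
- Change: SE = √(200/30) = 2.58, 6/2.58 = 2.32, Φ(2.32 − 1.99) = 63% at any ρ.
- Adjusted, paired (28 df, critical value 2.05): at ρ = 0, Φ(3.29 − 2.05) = 89%. At ρ = 0.28, SE = √(128/30) = 2.07 and Φ(2.90 − 2.05) = 80%. Simulation gives 87% and 79%, because slope and error are estimated from 30 pairs.

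**Simulated power, 20,000 trials per scenario.** Tukey means a significant interaction, then gel below sponge on post means. The other columns require all three contrasts. Reliability is participant variance/169.

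| ρ | Reliability between visits | Tukey | Change | Post only | Adjusted |
|---|---|---|---|---|---|
| 0 | 119/169 = 0.70 | 59% | 63% | 90% | 87% |
| 0.28 | 99.6/169 = 0.59 | 42% | 63% | 80% | 79% |
| 0.5 | 69/169 = 0.41 | 27% | 63% | 64% | 75%* |
| 0.7 | 2.3/169 = 0.01 | 14% | 63% | 43% | 70%* |

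*Pooled error, participant fixed. The first two adjusted figures use contrast-specific error.

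The last two rows are a sensitivity range only. They imply low reliability between visits, whereas the protocol (Pre/post tDCS assessments) describes test-retest reliability as excellent, without a figure.

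**Other advantages, ρ = 0/0.28.** At 4 points (12 vs 8): Tukey 20/13%, change 33%, adjusted 55/45%. At 8 points (20 vs 12): Tukey 90/77%, change 87%.

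**False claims, gel = sponge = 12, shams 0.** Equal SDs: planned sequence 0.1–0.2%, three contrasts about 2.5%. With sham change SDs about half the active ones, one pooled error gives about 5–6% (4.3–4.7% at 7 against 10). Contrast-specific error keeps it at about 2–3%.

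**The case against.** The strongest defence is that the plan is sound as far as it goes. The interaction addresses change. Under random order, pre-stimulation means are equal in expectation, so post-versus-post pairs estimate the right quantity. H2A already states a conjunction, and 0.05 is set for every analysis, so an all-three rule mostly restates the protocol. All of this stands. What is missing is the link from that conjunction to a test.

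A second objection is that ignoring the pre value is not the main source of loss. This also stands: at low ρ, three named contrasts on post values alone reach 90% and 80%, so the gain over Tukey comes from not paying for 28 pairs. Plain change scores barely beat Tukey at ρ = 0 (63 against 59%) and do slightly worse there at an 8-point advantage (87 against 90%). That is a reason to adjust for the pre value rather than analyse change. It does not rescue Tukey, which remains far below the adjusted contrasts.

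Third, the inputs come from a small, more impaired gait sample, and the 6-point advantage is assumed. That limits the figures but not the structural point.

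**Conclusion.** The point holds as one of lost power and an open choice of test, and should be fixed. The follow-up contains no comparison equal to a difference in pre-to-post change, and H2A is tied to no test. Under the stated assumptions the most favourable Tukey reading has about 59% power at ρ = 0 and 42% at ρ = 0.28, against about 87% and 79% for three pre-value-adjusted contrasts. These figures apply to gait speed only.

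A reader might infer three stronger things that the documents do not support:
- That the plan is biased or inflates false claims. The post-versus-post reading is unbiased, and its false-claim rate in the equal-SD case is 0.1–0.2%.
- That the primary model ignores change. The interaction tests it jointly.
- That power falls to 14%. This needs ρ = 0.7, where reliability between visits would be 0.01, against the protocol's own description of its procedures.

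**What to change.** Keep the two-way model and its covariates ("Age, sex, and BMI will be included as covariates because each is associated with one or more metrics of standing or walking"). Keep Tukey for all other pairs, including conventional tDCS against sham, and for the secondary outcomes ("Similar analyses will be applied to the secondary outcomes"). Add to the SAP:

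> For each primary outcome, H2A is tested by three pre-specified contrasts: gel-tDCS vs sponge-tDCS, vs gel-sham and vs sponge-sham. For each, the within-participant difference in the immediate post-stimulation value is regressed on the difference in the pre-stimulation value from the same visits. The intercept is the contrast and is tested with that contrast's own error. H2A is supported for that outcome only if all three contrasts favour gel-tDCS at the two-sided 0.05 level. This is the primary analysis for H2A.

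Age, sex and BMI are constant within a participant, so their main effects cancel in these paired contrasts. A mixed model with condition-specific variances would also serve, but the SAP should name one model and offer no alternative. A single pooled error should be avoided, because Hypothesis 2B itself predicts that variability differs between the two active conditions.

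The change costs one paragraph and no new data. Because all three contrasts must succeed, power stays modest for small advantages: about 55% and 45% at 12 vs 8 for ρ = 0 and 0.28. The false-claim rate rises from 0.1–0.2% to about 2.5%, the nominal one-sided level. Under unequal SDs it stays there only with contrast-specific error. How results combine across the primary outcomes is a separate point.
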